## Brief Summary/Abstract

Contrast-enhanced spectral mammography (CESM) is an FDA approved tool for breast cancer detection. However, adoption into clinical practice has been slow. In this study, we will explore patient issues related to the use of CESM for breast cancer screening. After receiving the first 50 results from another study (IRB-HSR# pending, Submission #11378) survey of women with dense breasts presenting for screening mammography to understand issues related to convenience, risks, and benefits of advanced screening, we will proceed with this (CESM) study. For this study, 210 women with heterogeneous or dense breast tissue reported on a previous mammogram, will be recruited to undergo a screening Contrast-enhanced Spectral Mammography (CESM). The CESM will serve as the subject's annual screening breast exam for clinical care. A survey will be administered before and after the examination that evaluates the patient experience. Women will not be at high risk for breast cancer (<20% lifetime risk). All abnormal findings will be acted upon independently. Results of the general screening population survey will be compared with those of women who choose to undergo the CESM examination in order to evaluate the influence of age, education, and lifetime risk on decision making about advanced screening.

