**2. List the criteria for exclusion for CESM**

- No mammogram within last 24 months
- Fatty or scattered fibroglandular tissue on last mammogram
- History of allergy to iodinated contrast
- History of renal disease or renal function abnormalities
- Pregnant women
- History of diabetes

- History of paraproteinemia syndromes such as multiple myeloma
- History of collagen vascular disease
- History of vascular disease (coronary artery disease, myocardial infarction, carotid disease, peripheral vascular disease, or known visceral artery disease)
- Previously identified as high risk for breast cancer (>20% lifetime risk)
- Asthma
- Sickle Cell Anemia
- Currently on Dialysis
- If patient is age 60-69 years we will need to confirm that kidney function is normal. We will draw a small volume of blood and check this, unless patient has had a lab test showing normal kidney function in the last 30 days as part of standard of care.

**4. List any restrictions on use of other drugs or treatments.** none

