**3. Provide a justification for the sample size used in this protocol.**

We have funding for 210 screening CESM subjects. This should allow us to evaluate for general attitudes toward CESM as well as some sub-analyses related to factors such as age, and family history. More specifically, we should be able to estimate the percentage of women who have a positive attitude toward CESM within  $\pm 3.5$  percentage units. This includes the worst case scenario in which the percentage is 50%, which is the scenario in which a binomial outcome variance is maximized.

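### Lifetime risk is studied as an influence on choosing CESM by comparing CESM women with a general screening survey, yet known high lifetime risk bars entry to the CESM group; unless the survey has the same limit, eligibility is confounded with choice

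*Protocol*

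**What the plan says.** The Brief Summary/Abstract fixes the comparison, "Results of the general screening population survey will be compared with those of women who choose to undergo the CESM examination", and how it is to be read: "in order to evaluate the influence of age, education, and lifetime risk on decision making about advanced screening".

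The two sides are described differently.

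- **Survey side.** It comes from a separate submission and is called a "survey of women with dense breasts presenting for screening mammography". The Protocol does not reproduce that study's age, risk or health criteria.
- **CESM side.** The same section says "Women will not be at high risk for breast cancer (<20% lifetime risk" (closing bracket cut from the quote). Inclusion/Exclusion Criteria, item 1, limits age to 40 to 69. Item 2 excludes women "Previously identified as high risk for breast cancer (>20% lifetime risk" (bracket again cut), and also lists medical exclusions, among them "History of diabetes", vascular disease, renal disease, asthma and collagen vascular disease. The group size is set by money: "We have funding for 210 screening CESM subjects".

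Statistical Considerations, item 5, plans a logistic regression of willing (1) against unwilling (0) on age, education and breast cancer risk factors, tested at 0.05. It does not say where the unwilling women come from, and its listed predictors contain no eligibility term. Nothing in the Protocol narrows the survey respondents to women who could have had CESM.

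**The concern.** A comparison of takers with a general population shows influence on choice only if both sides had the choice. Here a factor under study is also an entry rule for one side. If the survey contains women known to exceed 20% lifetime risk, they cannot have counterparts in the CESM group, whatever they would have preferred. The contrast then shows fewer high-risk women among those who chose CESM, and the stated purpose invites reading this as an influence of risk on the decision.

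The study exists to understand attitudes and barriers to screening CESM. Reporting its own entry rule as a barrier would mislead on that question. If higher-risk women were in fact keener on advanced screening, a contrast of known high risk, yes or no, could not show it, because the CESM count is zero by design. How far that could mislead has not been quantified.

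Age and education are touched less directly, through the age limits and the medical exclusions.

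**Working it through.** The Protocol gives no figure for this comparison, so there is nothing to reproduce. The check asks what the comparison shows when choice among eligible women does not depend on age, education or risk.

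**Inputs from the Protocol.** 210 CESM women; none known to exceed 20% lifetime risk; ages 40 to 69; significance level 0.05.

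**Inputs assumed.** The survey has no risk or health limit. Survey size is 50, 210 or 500. The share known to exceed 20% is 2% to 10%. The survey total is not given; the 50 in the Brief Summary/Abstract is the number of results awaited before this study starts.

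**Step 1, one table.** With k high-risk women, all in the survey group, the probability of that table with margins fixed is C(50, k) / C(260, k), where 260 = 50 + 210. In both cases below this is also the two-sided Fisher p-value.

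- k = 5 (10%): 2,118,760 / 9.525 × 10⁹ = 0.0002.
- k = 2 (4%): 1,225 / 33,670 = 0.036.

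So two known high-risk respondents among 50 would already cross 0.05.

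**Step 2, chance of a false association.** Taking k as binomial and applying Fisher's test at two-sided 0.05:

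| Survey size | 2% high risk | 5% | 10% |
|---|---|---|---|
| 50 | 26% | 72% | 97% |
| 210 | 25% | 95% | 100% |

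**Step 3, all three factors together.** Simulated logistic regression of group (CESM 1, survey 0) on age, education and continuous lifetime risk, with Wald tests at 0.05 and 500 runs per setting. Survey ages are 40 to 69, so any age effect here comes from the medical exclusions alone. The scenarios are assumptions:

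- weak: 2% high risk, excluded conditions rising from 10% to 25% over ages 40 to 69, no link with education;
- middle: 5%, 15% to 40%, odds ratio 1.5 between education and the excluded conditions;
- strong: 10%, 15% to 50%, odds ratio 2.0.

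Rejection rates for age / education / lifetime risk:

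| Survey size | Weak | Middle | Strong |
|---|---|---|---|
| 210 | 9 / 6 / 9% | 18 / 10 / 33% | 32 / 18 / 84% |
| 500 | 8 / 4 / 9% | 26 / 8 / 37% | 40 / 25 / 93% |

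Simulation error near 5% is about one point: √(0.05 × 0.95 / 500) = 0.0097. Education therefore stays nominal when it has no link with the excluded conditions. Lifetime risk is the most affected factor in the middle and strong scenarios.

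**Step 4, after restriction.** With the survey group limited to women who meet the CESM criteria, the strong scenario at survey sizes 50 / 210 / 500 gives 5.0 / 4.4 / 4.6% for age, 4.6 / 4.4 / 5.8% for education and 5.8 / 4.8 / 4.6% for lifetime risk, with odds ratios of about 1.

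**Step 5, size of an age shift.** If the medical exclusions removed 10% of women in their 40s and 35% in their 60s (assumed rates), the ratio of women aged 60-69 to women aged 40-49 would fall to (1 − 0.35) / (1 − 0.10) = 0.72 of its screening-population value before anyone chose.

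**The case against.** The strongest objection is that the survey's criteria are not shown. A one-clause description that mentions no limits does not prove there are none. A reader might infer that high-risk and medically excluded women are barred from the CESM side only; the Protocol does not establish that. If the survey has the same limits, the bias disappears. This stands, and the point is conditional on it. The word general, set beside the specific CESM criteria, makes the assumption reasonable but does not settle it.

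Second, a reader might infer that each ineligible survey woman is counted as having declined CESM. No section says so. Item 5 of Statistical Considerations codes willingness, so a high-risk respondent who says she is willing would be coded 1. This also stands: steps 2 and 3 describe the group comparison in the Brief Summary/Abstract, not a coding that the Protocol prescribes. That comparison is nonetheless given as evidence on decision making, so the confounding does not depend on the coding in item 5.

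Third, it is tempting to say that all three factors are biased. Only lifetime risk is affected by construction, and only as known risk, since the criterion covers women previously identified. Age needs a different survey age range or excluded conditions that vary with age. Education needs a link for which the Protocol offers no evidence.

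Fourth, choosing an analysis set is often left to a statistical analysis plan. That is fair for detail, but here the Protocol itself names both the comparator and the interpretation. The primary analysis, within the CESM group, is unaffected.

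**Conclusion.** The point holds in conditional form. If the survey has no lifetime-risk limit, the lifetime-risk contrast in the Brief Summary/Abstract is confounded by eligibility, and a difference arises without any effect of risk on choice. With 5% to 10% of survey women known to exceed 20%, the chance of a false association is 72% to 97% with 50 survey women and 95% to 100% with 210. At 2% it is about 25% with either size. The shares and survey sizes are assumptions, and these figures are for known high risk as a yes/no factor.

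Distortion of age is possible but indirect. Distortion of education is possible only through a link with the excluded conditions. The documents do not support a claim that all three associations must appear, or that the study's answer would be reversed.

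**What to change.** In the Brief Summary/Abstract, where the comparison is set out:

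1. Restrict the survey comparison group to respondents aged 40 to 69 and not known to exceed 20% lifetime risk, and without the medical exclusions of the CESM criteria where the survey records them.
2. State that conclusions on lifetime risk apply only at or below 20%.
3. Where the medical exclusions are not recorded, describe the comparison as one that does not separate eligibility from choice.

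If the survey already has the same criteria, one sentence saying so is enough.

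The cost is a short text change, a filter on the survey data and a smaller comparison group. The filter on age and known risk is cheap if the survey holds both. Filtering on medical conditions needs fields that may not exist, which is why the third step is a fallback. No procedure, recruitment step or entry rule changes.

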**1. Provide target # of subjects (at all sites) needed to complete protocol.**

- 210 CESM procedures at the Breast Care Center.

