## 5. What is your plan for secondary variable analysis?

1. We will evaluate differences by age, education, and risk factors as to whether these drive willingness to undergo CESM.

**Data summarization:** Binary risk factors will be summarized by frequencies and percentages. Continuous scaled risk factors will be summarized by the mean and standard deviation, the median and interquartile range, and the range of distribution.

**Statistical analyses:** Multivariate logistic regression will be utilized to determine if there is an association between the willingness to undergo CESM and age, level of education, and breast cancer related risk factors. The outcome variable will be binary and the value 1 will be assigned if the patient is willing to undergo CESM and the value 0 will be assigned if the patient is unwilling to undergo CESM. Predictor variables will include age, level of education, and breast cancer related risk factors. Type III Wald tests will be conducted to determine which predictor variables are uniquely associated with outcome. A  $p \leq 0.05$  null hypothesis rejection rule will be used as the bases for identifying unique partial associations.

2. A secondary endpoint will evaluate differences in recall and PPV for biopsy recommendation compared to our practice norms for women with dense breasts during the same time interval.

**Data summarization:** Recall frequencies and positive predicted values (PPV) will be summarized in the traditional manner by frequencies and percentages for the former, and by percentages for the latter.

**Statistical analyses:** Recall frequencies and PPV for biopsy recommendation will be compared between the two study-groups by way of exact binomial methods.

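### The drivers of the decision to have CESM are studied with two unreconciled contrasts, and the willing-versus-unwilling model has no named source of unwilling women

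*Protocol*

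**What the plan says.** Two places in the protocol address what drives the decision to have CESM.

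- **Brief Summary/Abstract.** "Results of the general screening population survey will be compared with those of women who choose to undergo the CESM examination", and the purpose is given as "in order to evaluate the influence of age, education, and lifetime risk on decision making about advanced screening". The survey belongs to a separate study and is described as a "survey of women with dense breasts presenting for screening mammography to understand issues related to convenience, risks, and benefits of advanced screening". Nothing removes women who would accept CESM from that group.
- **Statistical Considerations, question 5 (secondary variable analysis), item 1.** A logistic regression in which willing women are coded 1 while, for the others, "the value 0 will be assigned if the patient is unwilling to undergo CESM". Age, education and risk factors enter the model as predictors, and "Type III Wald tests will be conducted to determine which predictor variables are uniquely associated with outcome". The survey is not mentioned, and no source is named for the women coded 0.

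Three other places bear on this. The enrolment target is "210 CESM procedures at the Breast Care Center", and 210 is also the number who will sign consent. The Inclusion/Exclusion Criteria limit these women to ages 40 to 69, exclude a lifetime risk above 20%, and exclude a list of comorbidities. The Study Design section says that no controls are used.

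**The concern.** The two places ask one question and answer it with different reference groups: all survey respondents in one, unwilling women in the other. These contrasts estimate different quantities, so one factor can show a clear association in one and little in the other. The more acceptable CESM is to women in general, the more the survey group resembles the choosers, and the closer the Abstract contrast moves to no association. The study wants to know why uptake is slow, so a weak contrast could be misread as showing that age, education and risk do not matter.

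The willing-versus-unwilling model has a more basic problem. Every enrolled woman has agreed to CESM, so the trial by itself yields essentially no zeros.

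**Working it through.** The protocol gives no sample size, effect size or power for this comparison, so there is no figure of its own to reproduce.

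**Inputs.** From the protocol: 210 choosers and a two-sided 0.05 level. Assumed, because the protocol does not give them: 210 survey respondents, all eligible; a binary factor with 50% prevalence; a true willing-versus-unwilling odds ratio (OR) of 2.0; a willing share w from 10% to 90%; and choosers who represent willing women.

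**Step 1: what the Abstract contrast estimates.** Let p1 and p0 be the probabilities of being willing with and without the factor. They satisfy (p0 + p1)/2 = w and [p1/(1 − p1)] / [p0/(1 − p0)] = 2. At 50% prevalence, the odds of having the factor are p1/p0 among choosers and 1 in the whole survey population. The OR of choosers against all respondents is therefore p1/p0, a ratio of probabilities.

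Example at w = 50%: p0 = 0.4142 and p1 = 0.5858. The true OR is (0.5858/0.4142)² = 2.0, while the Abstract contrast gives 0.5858/0.4142 = 1.41.

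**Step 2: power.** With factor shares a and b in groups of size m and n, SE² = 1/(m·a) + 1/(m(1 − a)) + 1/(n·b) + 1/(n(1 − b)), and power is Φ(|log OR|/SE − 1.96) + Φ(−|log OR|/SE − 1.96).

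Example at w = 50%:
- 210 choosers (share 0.5858) against 210 respondents (share 0.50): log OR 0.347, SE 0.197, power 42%.
- The same choosers against the 105 unwilling respondents (share 0.4142): log OR 0.693, SE 0.243, power 82%.

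| Willing share | OR, choosers vs all respondents | Power, choosers vs all 210 | Unwilling among 210 | Power, choosers vs unwilling |
|---|---|---|---|---|
| 10% | 1.87 | 88% | 189 | 92% |
| 30% | 1.63 | 69% | 147 | 89% |
| 50% | 1.41 | 42% | 105 | 82% |
| 70% | 1.23 | 18% | 63 | 65% |
| 90% | 1.07 | 6% | 21 | 31% |

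About (1 − w) of the log OR remains. At 5% willing the OR is still 1.93, so the loss is small when few women are willing.

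**Step 3: several predictors.** A simulation of 400,000 women used true log ORs of 0.40, 0.70 and 0.50 for age, education and risk. Choosers against the whole population gave 0.27, 0.48 and 0.34 at 26% willing; 0.15, 0.28 and 0.20 at 58%; and 0.06, 0.11 and 0.08 at 84%.

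**Step 4: unequal eligibility.** Suppose 10% of survey women are above the risk limit, and a risk factor unrelated to willingness is present in 60% of them and 20% of the rest. Its survey prevalence is 0.1 × 0.6 + 0.9 × 0.2 = 0.24. Choosers show 0.20. The OR is (0.20/0.80)/(0.24/0.76) = 0.79, although the true OR is 1. In the simulation, cutting only the choosers to the lowest 90% of risk changed the risk log OR from the true 0.50 to 0.04, −0.05 and −0.15 at the three willing shares.

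**The case against.** - **The Abstract is a summary.** It defines no model, coding or test, and only the secondary analysis does. The two may be one analysis loosely described, with survey respondents supplying the zeros. That reading is possible, but no text states it, and the Abstract refers to the survey population as a whole. This limits the seriousness of the point without removing it.
- **A ratio of probabilities is a legitimate estimand.** It has the same null as the OR and fairly describes how a factor changes the chance of choosing CESM. This stands. The fault is that the two contrasts are not reconciled, not that one is invalid.
- **The size is unknown.** The survey's size, eligibility and willing share are not shown, nor is it shown whether it asks about willingness. This also stands. The figures are conditional, and the loss is slight at low willing shares.
- **Women who decline the nurse's invitation could be the zeros.** The protocol does not name them. It limits pre-screening questions to the eligibility criteria, which do not include education.

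A reader might infer that the Abstract contrast pulls every association toward no effect. The documents do not support that. It requires both groups to share one eligibility, and limits on age, risk and comorbidity are stated only for the choosers. Step 4 shows that a null factor can then appear associated and that a sign can reverse.

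A reader might also set the Abstract contrast against a power of 93-94%. That benchmark needs 210 unwilling women, who would not be available among 210 respondents of whom some are willing.

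**Conclusion.** The point stands as an unreconciled contrast plus an outcome category that the trial cannot fill. The overlap of willing women with the reference group would, by itself and under common eligibility, move each non-null association closer to 1: for an assumed OR of 2.0, from 1.87 at 10% willing to 1.07 at 90%. With eligibility as stated, the net bias for age and risk can go in either direction.

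These sizes rest on assumed values for prevalence, effect, survey size and willing share. The missing source of unwilling women rests on the text alone. This concerns a secondary question and leaves the primary outcomes (willingness to repeat CESM and to recommend it) untouched. It should be settled before the data are analysed.

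**What to change.** 1. State one contrast, willing versus unwilling, in both the Abstract and the secondary analysis.
2. In the secondary analysis, keep the 210 choosers as outcome 1. Name as outcome 0 the general-survey respondents who say they are unwilling and who meet the CESM inclusion and exclusion criteria.
3. In the Abstract, label the comparison of choosers with all respondents as descriptive.
4. If the survey does not record willingness, remove the claim about influence on decisions from the Abstract and drop the willingness model.

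**Cost.** Rewording and a recode of survey answers; no additional CESM examinations. The reference group becomes smaller, and the eligibility filter may shrink it further than the table shows. Even so, under the stated assumptions power is 92/89/82/65/31% at 10/30/50/70/90% willing, against 88/69/42/18/6% for choosers versus all respondents.

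The choosers should stay in the model. Fitting it to the 210 survey respondents alone, with w × 210 willing and (1 − w) × 210 unwilling women in the step 2 formula, gives 30/61/70/61/30%. At 10% and 30% willing that is less than the contrast it would replace. One limitation remains: outcome 1 would be an actual choice and outcome 0 a stated one, and the report should say so.

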## Background

[figure not shown]
### 1. Provide the scientific background, rationale and relevance of this project.

Screening mammography reduces breast cancer mortality by 15-40%. However, the limitations of mammography have long been known regarding the ability to detect cancer in women with dense breast tissue. Interval cancers, presenting as a palpable or other clinical finding between screening intervals, are 5 times more likely in women with heterogeneously dense breast tissue and 17 times more likely in women with extremely dense tissue compared with women with predominately fatty breasts (1). This lack of an effective breast cancer screening modality has prompted breast density legislation- now in effect in 19 states. In 2011, Virginia became the 3rd state to have a breast density law enacted. However, more than 25 million women age 40-74 years have either heterogeneous or dense breast tissue on mammography (2). Any decisions regarding supplemental screening may be costly to our society.

[figure not shown]
The most common ancillary screening test performed after a mammogram is a screening ultrasound (US). Screening US detects about 30% more breast cancers than mammography alone (3-5). However, screening US is associated with a high false positive rate. Whereas women undergoing screening mammography have a 1-2% risk of undergoing biopsy, 5-7% of women undergoing screening US will be recommended to undergo biopsy. The positive predictive value (PPV) of biopsy recommendation for lesions identified at screening US is also quite low (7-9% cancers, versus 25-40% for mammography). The low specificity is the major downside of using US for ancillary screening of women with dense breast tissue. The cost associated with this examination is high- for every 100 exams performed, up to 7 biopsies will be performed, and up to 10 will have another US in 6 months due to an indeterminate lesion.

[figure not shown]
Contrast-enhanced spectral mammography (CESM) is an emerging modality that incorporates both anatomic (structural) and functional (enhancement) information of the breasts. CESM is an FDA approved imaging study for detection of breast cancer and is frequently used for diagnostic patients in the UVa Breast Care Center.

There are less than 20 of these units in the U.S., and UVa Cancer Center Breast Program has one. In this exam, patients receive IV iodinated contrast, similar to having a CT scan. After 2 minutes, routine mammographic views are obtained. During the exposure, both high (45-49 kVp) and low (26-30 kVp) energy images are obtained (Figure 1). The low energy exposure is below the “k-edge” of iodine and so the appearance is the same as a conventional mammogram. This high energy exposure will “see” the iodine and the breast tissue. This high energy exposure is subtracted from the low energy exposure to generate an “iodine” image (Figure 2). Because the dense tissue is subtracted out, the CESM is not limited by dense tissue.

